Postural stability declines with aging (2). Previous studies have shown that dance interventions in many genres have had positive effects on postural stability in older adults, including genres such as contemporary dance (2), Argentine tango (3), traditional Greek dance (4), Pilates (5), and Latin dance (5). Kattenstroth suggests that a special dance program designed for older adults may lead to improvements in postural stability following the intervention (6). Ferrufino et al compared the effectiveness of a contemporary dance intervention with that of a fall prevention program and found that the dance intervention was more successful in improving postural stability (2). Additionally, Zhang et al found that older adults who dance also tend to have better postural stability than non-dancers (7), while Dewhurst et al found that older dancers have a reduced amount of regulatory activity needed to maintain postural stability (8). While studies have been conducted to examine postural stability in professional ballet dancers (9,10), few have examined the effects of a beginning ballet class for older adults on postural stability.

While the use of force plates for balance research is the gold standard, the use of Wii balance board alongside specialized balance software is a more affordable option which has surprisingly high reliability and validity for use in scientific research (11-13). As the early data from the Bridges to Skidmore research (IRB #1610-557) has demonstrated positive changes in balance following participation in dance, the use of Wii balance boards to more deeply understand the changes in balance in older adults appears to be an appropriate progression for this work.

Thus, the purpose of this current study is to examine the changes in postural stability in older adults following exposure to a beginning ballet dance technique course. It is hypothesized that a significantly reduced body sway will be observed in participants following a ballet dance training course over a 10-week period.

10. Human Participants:

A. Who are the participants?

Participants will be people ages 55 and up who agree to participate in a 10-12-week beginning ballet class program. Participants must be independent with activities of daily living (ADLs), require no walking aides, and be free from cardiovascular or neurological disease (5, 14-15).

Exclusion criteria will be active participation in a physical therapy program with the goal of improving functional mobility, missing six or more of the ballet classes offered during the 10-week period, receiving dance training in the past, not being independent with ADLs, using a walking aide, or diagnosis of cardiovascular or neurological disease. However, participants will not be excluded if they have a pacemaker if they are also cleared by a physician as a 'no restrictions' status for physical activity as indicated by the required intake form. Additionally, we will recruit a control group of adults ages 55 and up that will not participate in the dance class. As with the experimental group, control group participants must be independent with ADLs, require no walking aides, and be free from cardiovascular or neurological disease. Exclusion criteria for the control group will be participation in a physical therapy program with the goal of improving functional mobility, receiving dance training in the past, not being independent with ADLs, using a walking aide, or diagnosis of cardiovascular or neurological disease. The control and treatment groups are determined by the individuals themselves based on their desire to participate in the ballet classes.

B. How many participants do you plan to have in your study?

Each semester, we aim to recruit a convenience sample of up to 20 people for the control group and 20 people for the experimental group. We will cap the class at 20 each semester to assure a safe and appropriate ratio of students in the classroom. We aim to have one Skidmore dance student act as the lead teacher and be present at every ballet class, at least 1-2 additional Skidmore students assistant-teaching each class, and up to 20 individuals participating in the dance classes. Participants will be

responsible for finding transportation to campus and will be greeted by at least one participating Skidmore students at Dance Center entrance.

Participants may opt to leave the ballet classes and the study at any time. Participants who opt to withdraw from the study will not be asked to participate in the postural stability post-testing procedures.

Participants in the experimental group may choose to enroll in the beginning ballet class for more than one semester, though they are not required to. If they do, their participation number will remain constant throughout every semester of their participation in order to track changes in postural stability over longer periods of time. Every semester that a participant enrolls in the study, their postural stability will be assessed at the beginning and end of the semester just as for first-time experimental group participants. Additionally, control group participants may decide to join the experimental group at the beginning of a semester. However, experimental group participants may never participate in the control group in a later semester as they would meet exclusion criteria of prior dance training for that group.

C. How will the participants be contacted or recruited?

The PI will contact activities directors at senior centers and independent living communities in Saratoga Springs to inquire about having the ballet classes listed as activities with the PI's contact information so that interested parties may register for the class and receive more information about the corresponding research procedures. If granted permission, posters will also be put at these senior centers and independent living communities. Additionally, posters will be hung around Skidmore's campus to encourage participation, again with the PI's contact information so interested parties may register for the class and receive more information.

The control group will consist of people ages 55 and up who are not interested in taking a dance class but are willing to participate in the outcome measures of this study. As with the experimental group, the control group will be invited to participate by activities directors at senior centers and independent living communities and through self-nomination in response to posters hung in various locations. To participate, individuals will contact PI [name] via email to get more information and to register for the class. Any emails from the researchers to individuals encouraging them to participate, and prior to pre-and post-testing sessions, will include the following:

“Your decision to join this program or not join this program will not affect your relationship with Skidmore College in any way. If you decide that you do want to join the program, you can stop at any time. You can also choose not to participate at all or you can choose not to answer certain questions or do certain activities that we ask you to do. Also, you can stop participating in the program at any time without penalty or being in trouble in any way.”

D. Will the participants be compensated for participating? If so, describe:

Participants will not be compensated for their participation.

11. Procedures:

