Both the pre and post data collection will take approximately 15 minutes per participant at each testing session. Participants will receive instructions prior to each trial of 30 seconds with at least one research assistant spotting the participant should they lose their balance. Participants will be asked to stay in a static standing position for 3 trials of 30 seconds while standing on a Wii board in four of the following conditions : 1) bilateral stance with eyes open, 2) bilateral stance with eyes closed, 3) unilateral stance on the right limb 4) unilateral stance on the left limb. Participants will be given a 15 seconds rest period between each trial and will be told they may stop and rest at any moment during the testing process.

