11.3 Data Analysis

Five measures of postural stability were examined in this study: the area the CoP traveled through during each 30-second trial, the CoP displacement in the x- and y-planes during each trial, and the absolute value of the average speed of the CoP in the x- and y-planes through each trial. Non-parametric Wilcoxon signed ranks tests were used to compare these values at baseline and post-testing within each group, while non-parametric Mann Whitney U tests were used to compare the delta (post minus pre) values between groups for EO and EC trials.

12. Consent:

Participants will sign an Informed Consent must prior to beginning of any testing. Please see attached informed consent for details.

13. Risks and Debriefing:

The postural stability data collection offers minimal risk to participants. Fatigue and falls have been shown to be minimal in prior research (see background information on postural stability references) in older adults. To ensure no risk to participants, participants will repeatedly be reminded they may rest or stop at any moment, without penalty of any kind. As well, one 'spotter' will be present during all data collection trials to assist participants should they lose their balance.

The dance movements performed in the intervention sessions carry a minimal risk of injury. Ballet movements presented in the class will likely be outside of typical movement patterns and therefore hold some inherent risk, including slips, falls and muscle strains and sprains. To combat the likelihood of injury during the class, participants will be thoroughly instructed on the movement, technique, and expectations for each combination. The ballet class will be gentle with little to no aerobic activities, making this appropriate for all participants meeting our inclusion criteria. Additionally, while the class will be primarily instructed by the lead teacher, additional Skidmore students will be present to help decrease the risk of injury during the dance class. This way, each participant has additional support throughout the class time as needed.

If a serious injury occurs, the Skidmore Campus Safety will be called and/or 911 depending on the severity of the injury. If an injury occurs during testing off-campus, 911 will be called to appropriately treat the participant for any injury sustained.

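### The hypothesis names no comparator and section 11.3 does not tie the planned between-group test to it, so a sway reduction shared by both groups could confirm it.

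*Combined protocol and SAP*

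**What the plan says.** The hypothesis, stated in the background just before section 10, is that "a significantly reduced body sway will be observed in participants following a ballet dance training course over a 10-week period". The purpose sentence before it also speaks only of change after the course. Neither mentions controls.

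Section 10A sets up a concurrent control group that takes no class. Allocation is by choice: "The control and treatment groups are determined by the individuals themselves based on their desire to participate in the ballet classes". Section 10B aims, each semester, for "up to 20 people for the control group and 20 people for the experimental group".

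Section 11.2 gives the same balance task at pre- and post-testing: "Participants will be asked to stay in a static standing position for 3 trials of 30 seconds while standing on a Wii board", in four stance conditions.

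Section 11.3 begins "Five measures of postural stability were examined in this study" and then lists two kinds of test:

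- "Non-parametric Wilcoxon signed ranks tests were used to compare these values at baseline and post-testing within each group";
- "non-parametric Mann Whitney U tests were used to compare the delta (post minus pre) values between groups for EO and EC trials".

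It names no primary test, measure or condition, and no significance level.

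**The concern.** A control group serves to separate the effect of ballet from anything else that changes between the two test sessions. The hypothesis does not use it. As written, it is a before-and-after statement about those who danced, and the test that matches it most directly is the Wilcoxon test in the ballet group.

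If sway fell equally in both groups, that test could be significant and the hypothesis confirmed as worded, while the Mann-Whitney test showed no difference. The plan has no rule for which result stands. Nor does it guard against a related misreading, in which a significant result in the ballet group and a non-significant one in controls is taken as a group difference.

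At stake is the headline conclusion: the trial could report its hypothesis as confirmed on an uncontrolled comparison although it had a controlled one to hand.

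**Working it through.** **Step 1: set the texts side by side.**

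| Element | Where | Refers to controls? |
|---|---|---|
| Purpose | Background, before section 10 | No |
| Hypothesis | Background, before section 10 | No |
| Wilcoxon, pre v post | 11.3 | Run in each group separately, no contrast |
| Mann-Whitney on post minus pre | 11.3 | Yes, ballet v control |
| Rule linking a test to the hypothesis | None found | – |

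Suppose both groups have the same true reduction. The ballet Wilcoxon test addresses whether the ballet reduction is zero; it is not, so the test can rightly be significant. The Mann-Whitney test addresses whether the reductions differ; they do not. The hypothesis as worded is met by the first result. This step needs no numbers.

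**Step 2: illustrate the size.** The plan has no power or error figure to reproduce. Inputs:

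- 20 per group, from section 10B. This is a per-semester target, not the study size.
- Assumed, because the documents give none of them: no ballet effect; change scores normal with SD 1 and mean −g in both groups; two-sided 0.05; one measure in one condition; g from 0 to 0.5 SD.

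Simulation with 20,000 trials per value of g, as % of trials:

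| Shared gain g (SD) | 0 | 0.1 | 0.2 | 0.3 | 0.5 |
|---|---|---|---|---|---|
| Ballet Wilcoxon significant for reduced sway | 2.3 | 6.2 | 13.0 | 23.6 | 54.2 |
| Mann-Whitney significant favouring ballet | 2.4 | 2.6 | 2.4 | 2.5 | 2.5 |
| Ballet Wilcoxon significant, Mann-Whitney not favouring ballet | 1.6 | 4.9 | 11.2 | 21.4 | 51.8 |
| Ballet Wilcoxon significant, control Wilcoxon not | 2.3 | 5.8 | 11.4 | 18.1 | 25.0 |

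Hand check on the first row: with known SD, the chance of significance in the favourable direction is Φ(g√n − 1.96). At g = 0.3 and n = 20, 0.3 × 4.472 − 1.96 = −0.618, so about 27%. At g = 0.5, 0.5 × 4.472 − 1.96 = 0.276, so about 61%. The simulated values are somewhat lower, as expected for a rank test at this sample size.

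**Step 3: vary the group size.** First row only, for the same values of g:

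- 10 per group: 2.6/4.2/8.1/12.8/28.5%.
- 40 independent people per group, as if two full semesters were pooled: 2.5/8.6/22.9/44.2/85.3%.

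The Mann-Whitney rate stays at 2.1 to 2.5% in both cases.

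**Step 4: relax equal gains.** The 2.5% holds only if gains unrelated to ballet are the same in both groups. With assumed non-ballet gains of 0.5 SD in the ballet group and 0.2 SD in controls, at 20 per group, the Mann-Whitney test falsely favours ballet in about 14% of trials. At 0.5 v 0.3 SD the figure is about 8%.

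**Step 5: does naming the between-group test settle the matter?** Not alone. Five measures × two conditions (EO and EC) = 10 between-group tests. If they were independent and there were no true differences, the chance of at least one false result favouring ballet would be 1 − 0.975^10 = 22.4%; positive correlation lowers it. The deciding comparison therefore has to be a single one.

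**The case against.** The strongest reply is that the safeguard already exists. Controls are recruited and the change scores are to be compared between groups, so a shared gain would show in the trial's own results. This stands and limits the weight of the point. A reader might infer that the trial has no controlled analysis, or that the investigators mean to rest their claim on the within-group result. The documents support neither: the between-group test is in section 11.3, and nothing says it will be disregarded. What remains is that two results may conflict with no rule for choosing between them.

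Second, the hypothesis may be read as descriptive, in which case a before-and-after test matches it. That is a fair reading of the sentence. But the background presents the study as addressing the effects of a ballet class, and recruiting controls points to a comparison.

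Third, the shared gain is assumed. A reader might infer from the repeated board trials in section 11.2 that a learning effect is established. It is not: the section describes repeated testing and reports no learning. This stands, so the larger percentages are illustrations and not predictions.

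Fourth, section 11.2 also includes "3) unilateral stance on the right limb 4) unilateral stance on the left limb", and a reader might infer that the between-group analysis omits these stances. The wording of 11.3 is ambiguous about what the EO and EC qualifier covers, and coverage of stances is a separate question. It forms no part of this point.

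**Conclusion.** The concern holds as a gap in priority, not as a missing analysis. It is certain from the text that the hypothesis has no comparator and that section 11.3 assigns no test to it. A significant Wilcoxon result in the ballet group would then confirm it even if controls improved equally.

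The practical size is uncertain. Under the stated assumptions at 20 per group, it runs from negligible with no shared gain to about 54% at 0.5 SD, and is about 6 to 24% for gains of 0.1 to 0.3 SD. The contrasting 2.5% for the Mann-Whitney test rests on equal non-ballet gains, which self-selected groups do not guarantee. It would be too strong to say that the between-group test isolates a ballet effect; it removes only what the two groups share.

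The change should be made. The study is not invalid without it, but its conclusion is undefined when its two tests disagree.

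**What to change.** 1. Reword the hypothesis: the reduction in body sway from pre- to post-test is greater in the ballet group than in the control group.
2. State in section 11.3 that the between-group comparison of change decides the hypothesis. Name one of the five measures and one condition (EO or EC) as the deciding comparison, and call the rest secondary.
3. State that the within-group Wilcoxon tests are descriptive, and that significance in one group only will not be read as a group difference.
4. State the limits. The rule does not remove confounding from self-selection (section 10A), or unequal prior exposure to the board from repeat enrolment and from controls who later join the class (section 10B).

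The cost is a few sentences, with no new data and no new test. A positive claim becomes harder to reach, and nine of the ten EO and EC between-group comparisons become secondary.

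Section 11.3 is written in the past tense. If data have already been analysed, keep the present hypothesis visible and report the rule, including the choice of measure and condition, as dated and post hoc.

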11.1 Beginning Ballet Class Information

One-hour ballet classes will be held twice per week in one of the two dance studios or in the dance theater at Skidmore College. [name] '20 will serve as the lead teacher for each dance class from February 4th-April 26th. Other Skidmore students may serve as lead teacher in future semesters as determined by the PI and/or [name]. Each week the participants will partake in 120 minutes of ballet dance training, starting with warm-up exercises at the barre and then working towards learning combinations in the center. Participants may take short breaks to get a drink or use the bathroom as they need. Chairs will be set up in the dance studio or dance theater so individuals can rest

or take a break if they wish. They will learn the basic positions and combinations used in ballet, including: Plié, Tendu, Degagé, Rond de Jambe, Frappé, Chassé, Sauté, Pas de Bourrée, Glissade, and Révérence. Additional ballet movements and patterns may be employed as well. If a participant chooses not to dance for the full duration of a given class period, an assistant teacher may assist them out of the studio to wait comfortably in the lobby of the dance center, dance gym or sports center until the class ends and their transportation arrives if needed. They may also rejoin the class at any time, should they choose. Attendance will be taken at the start of each class to ensure that participants do not miss six or more classes in line with our exclusion criteria. Attendance will be documented in a password-protected electronic file through the participants' number IDs alongside the initials of their first and last name to maintain anonymity of the attendance document. Only [name], [name], and the lead teacher will have access to the attendance roster each semester.

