11.2 Data Collection

Data collection will take place at the dance conference room (Williamson Sports Center), the Human Performance Teaching Lab (Sports 101, Williamson Sports Center), multipurpose room (Williamson Sports Center), the intramural gym (Williamson Sports Center), or at the Prestwick Chase facility or the Saratoga Senior Center (if requested by an activities director) prior to the start of the ballet classes each semester with post-testing to be completed the week of, or following, the final ballet class of the semester. Tests of postural stability will be verbally explained/instructed to create clear expectations for the test and to help decrease any fear or anxiety surrounding the process.

Data collection will be conducted by [name] '19 with help from [name] as needed. Following the Spring 2019 semester, [name] will lead data collection and/or find another Skidmore student to help with data collection who is trained with this protocol. [name]

[name] will be contacted as needed to ensure the proper functioning of the data collection system/protocol. [name] has already received training in the data collection procedure from [name] and [name] from a prior research investigation examining postural stability in novice collegiate dancers (IRB 1712-683). Once calibrated, the use of balance boards to collect data on postural stability requires very little technical skill, and therefore it is appropriate for a trained student researcher to lead this process. Any additional student data collectors present will only be there to assist and guard the participants from falling. Student data collectors will be trained in all procedures and techniques directly by the PI or supervising faculty members prior to any data collection and must be able to demonstrate competency in testing prior to administering any tests on participants.

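### The attendance exclusion removes low attenders from the ballet group only, after baseline, and no analysis of everyone enrolled is planned.

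*Combined protocol and SAP*

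**What the plan says.** - **Ballet exclusions (section 10.A).** The list includes "missing six or more of the ballet classes offered during the 10-week period". The other items on it can be judged at entry.
- **Control exclusions (section 10.A).** The list is given separately: "Exclusion criteria for the control group will be participation in a physical therapy program", followed by past dance training, lack of independence in daily living, use of a walking aid, and cardiovascular or neurological disease. It has no attendance or adherence item.
- **Enforcement (section 11.1).** Attendance is recorded at each class "to ensure that participants do not miss six or more classes in line with our exclusion criteria".
- **Timing (section 11.2).** Testing takes place "prior to the start of the ballet classes each semester with post-testing to be completed" around the last class.
- **Withdrawal (section 10.B).** "Participants who opt to withdraw from the study will not be asked to participate in the postural stability post-testing procedures". This applies to both groups.
- **Analysis (section 11.3).** "Non-parametric Wilcoxon signed ranks tests were used to compare these values at baseline and post-testing within each group", and Mann-Whitney U "tests were used to compare the delta (post minus pre) values between groups for EO and EC trials". No analysis set, all-enrolled analysis, sensitivity analysis or handling of missing post-tests is given.
- **Hypothesis (background, before section 10).** The expectation is that "a significantly reduced body sway will be observed in participants following a ballet dance training course over a 10-week period".

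**The concern.** An exclusion that depends on how many classes a person misses cannot be an entry criterion, because nobody has missed a class at baseline. It removes people after they have been enrolled and measured, and it does so in one group only.

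If absence is related to how sway changes over the term, the ballet participants who remain are a selected sample. For example, illness or injury during the term might both keep people away and worsen their balance. Their post-minus-pre changes would then look better than those of the group that started, even if ballet did nothing. Controls who had the same illness or injury would stay in unless they chose to withdraw.

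The distortion would enter the between-group Mann-Whitney test and the ballet-group Wilcoxon test. The control-group Wilcoxon test is untouched.

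**Working it through.** **Does the rule act after baseline, and in one group only?** Yes. Section 11.2 puts the first test before classes, section 11.1 applies the rule from the class register, and section 10.A lists it for the ballet group alone.

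**What attendance does it require?** Section 11.1 gives two classes a week, so 10 weeks is 2 × 10 = 20 classes. A participant stays in with at most 5 misses, that is 15/20 = 75%. If the rule were counted over 12 weeks, it would be 2 × 12 = 24 classes and 19/24 = 79%.

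**How many people might it remove?** The documents give no absence rate, so the rates below are assumptions. The share is P(X ≥ 6), with X the number of missed classes. It is binomial if absences are independent, and beta-binomial if they cluster within people (intraclass correlation, ICC, 0.1 to 0.2).

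| Absence per class | 20 classes, independent | 20 classes, ICC 0.1 to 0.2 | 24 classes, independent | 24 classes, ICC 0.1 to 0.2 |
|---|---|---|---|---|
| 10% | 1.1% | 8.6-12.0% | 2.8% | 12.6-15.3% |
| 15% | 6.7% | 17.1-20.1% | 13.9% | 23.7-25.0% |
| 20% | 19.6% | 27.6-29.0% | 34.4% | 35.2-36.4% |

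The loss could be negligible or large.

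**How large a shift follows?** Let r be the correlation between attendance and improvement, and q the fraction of lowest attenders removed. In a large sample the mean improvement of those kept is shifted by r·φ(z_q)/(1 − q) SD. At q = 0.20, z_q = −0.842 and φ = 0.280, so the multiplier is 0.280/0.80 = 0.350. The shift is 0.2 × 0.350 = 0.070 SD at r = 0.2 and 0.5 × 0.350 = 0.175 SD at r = 0.5. With exactly 4 of 20 removed, the finite-sample values are 0.066 and 0.167 SD.

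**What does this do to the tests?** The plan states no error rate or effect size to reproduce, so this is a Monte Carlo illustration (200,000 runs per cell). It assumes:
- no true effect;
- 20 enrolled per group, the recruitment ceiling in section 10.B;
- normal change scores, signed so that positive means less sway;
- the k lowest attenders removed from the ballet group, and no other losses;
- two-sided 5% tests by normal approximation with continuity correction.

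Each cell gives the values for r = 0.2 / 0.3 / 0.5.

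| Removed (k of 20) | Shift (SD) | Mann-Whitney, in favour of ballet (%) | Ballet Wilcoxon, in favour (%) | Mann-Whitney, total two-sided (%) |
|---|---|---|---|---|
| 1 (5%) | 0.019 / 0.029 / 0.050 | 2.73 / 2.87 / 3.31 | 2.73 / 2.97 / 3.71 | 4.75 / 4.80 / 5.01 |
| 2 (10%) | 0.037 / 0.054 / 0.091 | 3.12 / 3.52 / 4.38 | 3.14 / 3.69 / 5.13 | 4.98 / 5.13 / 5.74 |
| 4 (20%) | 0.066 / 0.099 / 0.167 | 3.55 / 4.28 / 6.69 | 3.96 / 5.21 / 9.13 | 4.99 / 5.39 / 7.44 |
| 6 (30%) | 0.096 / 0.143 / 0.237 | 4.25 / 5.63 / 9.51 | 4.43 / 6.38 / 12.65 | 5.47 / 6.54 / 9.99 |

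The Monte Carlo standard error is about 0.04 percentage points at 3% and 0.07 at 10%.

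**Reference points.** The nominal rate in favour of ballet is 2.5%. At r = 0 there is no shift, and the simulated rates are 2.28-2.39% (Mann-Whitney) and 2.05-2.23% (Wilcoxon). At r = −0.3 the shift reverses to −0.03 to −0.14 SD, and false Mann-Whitney findings against ballet are 2.9-5.7%.

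**The case against.** - **The rule defines exposure.** The study asks what happens after taking a ballet course, and attending 15 of 20 classes is a defensible completer definition. Controls attend no classes, so they could not have an attendance rule. This stands, and it is a good reason to keep the threshold as a labelled subset. It does not justify making that subset the only population the plan implies.
- **The groups are self-selected.** An all-enrolled analysis therefore protects no randomised comparison, and confounding by choice of group is probably the larger problem. This also stands. The attendance rule is nonetheless a second, separate selection step. It reaches the ballet within-group test as well, and unlike self-selection it can be removed by rewording.
- **The bias may be small or absent.** With no true effect, attendance and change can be related only through a common cause, and absence for reasons such as transport need have nothing to do with sway. Total two-sided Mann-Whitney error is 4.8-5.4% at r = 0.2 to 0.3 with up to 20% removed, which is close to nominal. This limits the weight of the point. The near-nominal total does hide a move of errors towards one side, and that side is the hypothesised one when r is positive.
- **Removal from the analysis is inferred.** Section 11.3 does not say that low attenders are dropped, and no section says that they are not post-tested. Removal is the natural reading of an exclusion criterion, and the text should settle it.
- **The remedy is partial.** Low attenders who withdraw still have no post-test. This is correct, and the illustration, which assumes no other losses, shows the most that could be recovered.

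**Conclusion.** The concern holds. The asymmetry is certain from the text: one group is conditioned on behaviour after baseline, the other is not, and no analysis of everyone enrolled is named. The consequence is conditional. It needs absence to be related to change in sway, and neither its size nor its direction can be read from the documents. Across the assumed range (5 to 30% removed, r = 0.2 to 0.5) the spurious shift is 0.02 to 0.24 SD. The top of that range needs both r = 0.5 and 6 of 20 removed. The point should be fixed because the bias is avoidable and cheap to avoid, but it ranks below confounding from self-selected groups.

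A minor wording point goes with it. The rule counts misses in a 10-week period, the programme is described as lasting 10 to 12 weeks, and the stated dates of 4 February to 26 April span 82 days (taking the year as 2019). It is unclear whether absences after week 10 count.

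**What to change.** 1. Take the attendance item out of the exclusion criteria in section 10.A, and use it only to define an adherent subset. Amend section 11.1 to match.
2. Invite everyone who has not withdrawn from the study to the post-test, whatever their attendance. Unless the consent form already does so, separate stopping the classes from withdrawing from the study.
3. In section 11.3, make the main analysis all enrolled participants with a post-test, in the group they joined. Label the attendance-restricted analysis as a sensitivity analysis.
4. Report, by group, the number below the attendance threshold and the number of withdrawals, with reasons and baseline sway.
5. Reconcile the statements on programme length so that the adherent subset rests on one class count.

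**Cost.** A protocol wording change, about 15 minutes of post-testing per low attender (the session length in section 11.2), and one short table. The main estimate will be diluted by people who attended little, but the adherent-subset estimate is still reported beside it. Confounding by self-selection and the loss of withdrawers without a post-test remain.
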